## 8 CONVENTIONS

In general, EmBARC standard time windowing, imputation rules, and counting rules will be applied.

- For death dates, the following conventions will be used for imputing partial dates:
  - If only the day of the month is missing, the 1st of the month will be used to replace the missing day. The imputed date will be compared to the last known alive date and the maximum will be considered as the death date.
  - If the month or the year is missing, the death date will be imputed as the last known alive date.
  - If the date is completely missing but the reason for death is present, the death date will be imputed as the last known date alive.
- For date of progression after start of study therapy, the following conventions will be used for imputing partial dates:
  - If only the day of the month is missing, the 1st of the month will be used to replace the missing day. In case of the date of death is present and complete, the imputed progression date will be compared to the date of death. The minimum of the imputed progression date and date of death will be considered as the date of progression.
  - If the day and month are missing or a date is completely missing, it will be considered as missing.
  - For date of progression to prior therapies, the following conventions will be used for imputing partial dates:
    - If only the day of the month is missing, the 1st of the month will be used to replace the missing day.
    - If the day and month are missing or a date is completely missing, it will be considered as missing.
- For date of progression to prior therapies, the following conventions will be used for imputing partial dates:
  - If only the day of the month is missing, the 1st of the month will be used to replace the missing day.
  - If the day and month are missing or a date is completely missing, it will be considered as missing.
- For other partial/missing dates, the following conventions were used:
  - If only the day of the month is missing, the 15th of the month will be used to replace the missing day.
  - If both the day and the month are missing, “July 1” will be used to replace the missing information.
  - If a date is completely missing, it will be considered as missing.

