### **Progression Free Survival (PFS)**

The primary definition of PFS is defined as the time from the date of first dose of study medication to the date of first confirmed disease progression or death, or the time between date of randomization and the date of first documented progression or death for nivolumab/daratumumab cohorts. Subjects who remain alive and have not progressed will be censored on the last adequate tumor assessment date on or prior to the date of subsequent therapy. Allogeneic SCT and ASCT will be considered as subsequent therapy. Subjects who did not have any post-baseline efficacy assessment and did not die will be censored on the date of first dose of study medication or date of randomization for nivolumab/daratumumab cohorts.

The secondary definition of PFS (ITT definition) is defined as the time from the date of first dose of study medication to the date of first disease progression or death, or the time between date of randomization and date of progression or death. Subjects who remain alive and have not progressed will be censored on the last adequate tumor assessment date. Subjects who did not have any post-baseline efficacy assessment and did not die will be censored on the date of first dose of study medication or date of randomization for nivolumab/daratumumab cohorts.

For MM subjects, an adequate tumor assessment visit for ruling out progression will require the following information: Serum monoclonal paraprotein results, if measurable at baseline and Urine monoclonal paraprotein results, if measurable at baseline, or for subjects who do not have measurable serum and urine monoclonal paraprotein results, serum free light chain results, if measurable at baseline.

Sensitivity analyses will be performed based on an alternate censoring scheme to account for non-uniform and infrequent tumor assessment schedules. For this analysis, subjects will be censored on their last visit date, defined as the last date of dosing, tumor assessment or lab assessment, whichever occurs last.

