### Duration of Response

Duration of response will be only calculated for subjects with best overall response of objective response defined as above. The duration of response is defined as the time between the date of first documented objective response and the date of first documented disease progression, or death, whichever is earlier. Subjects who remain alive and have not progressed will be censored on the last adequate efficacy assessment date prior to subsequent cancer therapy. Allogeneic SCT and ASCT will be considered as subsequent therapy.

Sensitivity analyses will be performed based on an alternate censoring scheme (same as PFS censoring scheme) to account for non-uniform and infrequent tumor assessment schedules. For this analysis, subjects will be censored on their last visit date, defined as the last date of dosing, tumor assessment or lab assessment, whichever occurs last.

Duration of response will be evaluated for responders (PR or CR for lymphoma subjects; SCR, CR, VGPR, or PR for myeloma subjects) only.

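### The SAP sets a day-missing on-study progression date to the 1st of the month with no lower bound, so it can precede randomization, a clean assessment or the first response

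*SAP*

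**What the plan says.** SAP section 8 (Conventions) has a rule for on-study progression: "For date of progression after start of study therapy, the following conventions will be used for imputing partial dates". If only the day is missing, the 1st of the month is used. If a complete death date exists, the two are compared: "The minimum of the imputed progression date and date of death will be considered as the date of progression". No other comparison is made.

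The death-date rule in the same section also starts from the 1st of the month but adds a floor: "The imputed date will be compared to the last known alive date and the maximum will be considered as the death date".

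The endpoints that use the progression date are in SAP 4.2.2. PFS in the nivolumab/daratumumab cohorts is "the time between date of randomization and the date of first documented progression or death for nivolumab/daratumumab cohorts". Duration of response is "the time between the date of first documented objective response and the date of first documented disease progression, or death, whichever is earlier". Neither definition, nor the censoring scheme in Table 1, bounds an imputed progression date from below.

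**The concern.** The 1st is the earliest day the recorded month allows. If randomization, an adequate assessment without progression, or the first response falls later in that month than the 1st, the imputed progression precedes it. Three kinds of wrong value can follow: a PFS time that ends before it starts, a duration of response that ends before the response, and a progression date that an adequate assessment on file contradicts. A date before randomization also conflicts with the rule's own scope, which is progression after study therapy began.

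The floor used for deaths shows that the authors saw the need for a plausibility check, so its absence for progression looks like an omission. Without a written rule, the programmer must decide what to do with an impossible interval after seeing open-label data.

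**Working it through.** The plan states no figure on this point, so there is none to reproduce. The check applies the rule as written to calendar dates.

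**Inputs.** Imputed day = 1st of the month; upper bound = complete death date (SAP section 8). PFS starts at randomization and duration of response at first response (SAP 4.2.2). Myeloma laboratory assessments are every 4 weeks from Cycle 1 Day 1 (Protocol 3.1). Assumption: true progression is equally likely on any calendar day, and a missing day is unrelated to the date.

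**Step 1: size of the shift.** Shift = day of month − 1. In a 365-day year the shifts sum to 7 × 465 (31-day months) + 4 × 435 (30-day months) + 378 (February) = 5,373, and 5,373/365 = 14.7 days. Listing every day of 2018–2021 also gives a mean of 14.7; the maximum is 30. The shift is never later.

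**Step 2: does the death bound help?** If death is on or after true progression, the 1st of the progression month cannot be later than death. Over all dates in 2018–2021 with consistent death dates, the bound acted 0 times. It matters only when the data are already inconsistent.

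**Step 3: how often is an earlier anchor overtaken?** Let the anchor (clean assessment, response or randomization) be g days before true progression. Imputed progression is strictly before it when day − 1 > g, and on or before it when day − 1 ≥ g.

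| Gap g (days) | Strictly before | On or before |
|---|---|---|
| 30 | 0% | 1.9% |
| 28 | 4.9% | 8.0% |
| 25 | 14.6% | 17.9% |
| 21 | 27.7% | 31.0% |
| 14 | 50.7% | 54.0% |
| 7 | 73.7% | 77.0% |

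At g = 28, strictly before means progression on day 30 or 31: 11 + 7 = 18 days, and 18/365 = 4.9%. Including ties adds the 11 dates on day 29: 29/365 = 7.9% in a common year, 117/1,461 = 8.0% over the four years. Only the 28-day row is the protocol schedule. The shorter gaps need an early, unscheduled, clinical or imaging finding.

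**Step 4: dated examples.** Intervals are simple differences in days. The floor column uses the day after the anchor.

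| Anchor | True progression | Imputed | True interval | SAP rule | With floor |
|---|---|---|---|---|---|
| Randomized 2 Mar 2019, no assessment between | 30 Mar | 1 Mar | 28 | −1 | 1 |
| First response 2 May 2019 | 30 May | 1 May | 28 | −1 | 1 |
| Response or clean unscheduled visit 9 May 2019 | 30 May | 1 May | 21 | −8 | 1 |

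If intervals are counted with one day added, the SAP-rule values become 0, 0 and −7, which are still not valid durations.

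**Step 5: Table 1.** Progression after subsequent therapy starts is censored at the last tumor assessment up to that start. Suppose therapy starts on the 10th and progression is on the 20th of the same month with the day missing. The true order gives a censored subject; the imputed date, the 1st, gives an event.

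**The case against.** The strongest case against is that this will rarely happen and little depends on it.

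- **Scheduled visits limit it.** The first scheduled on-treatment laboratory assessment is about 28 days after Cycle 1 Day 1, so a negative PFS depends mainly on unscheduled, clinical or imaging progression. Response needs two consecutive assessments (Protocol 3.1 and 5.4.1.2). On schedule, progression therefore comes about 56 days after first response, beyond the reach of a shift of at most 30 days. A negative duration of response needs early or unscheduled confirmation. This stands. The visible text sets no minimum confirmation interval, so the case is unusual but not excluded.
- **Partial dates should be few.** Cohort B serum and urine results come mainly from a central laboratory and normally carry a full sample date. This is plausible, but the documents give no count.
- **A company standard may cover it.** Section 8 opens: "In general, EmBARC standard time windowing, imputation rules, and counting rules will be applied". Its content is not in the documents, so a consistency check there cannot be ruled out. The explicit study rule has none, and a programmer would follow the explicit rule.
- **PFS and duration of response are descriptive.** The study is not powered for hypothesis testing and the primary endpoints are safety. This limits the consequence but does not make a negative duration acceptable.

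A reader might also infer that responders are lost from best overall response because their response would postdate the imputed progression. The documents do not support this. The SAP takes best overall response from the investigator's entry on the case report form and assesses ORR in these cohorts by investigator only. Nothing says that response is re-derived against an imputed date.

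**Conclusion.** The point holds as a minor error in a stated rule. As written, SAP section 8 can place progression before randomization, before an adequate clean assessment or before the first response, and the only bound it has does nothing on consistent data. Each imputed date is moved earlier or left unchanged, by 14.7 days on average, and the move can change a censored subject into an event under Table 1.

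On an exact 28-day schedule about 4.9% of imputed dates fall strictly before the previous assessment (about 8% with ties). These are shares of day-missing progression dates, not of subjects. They assume uniformly spread progression dates.

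Two stronger readings go too far. A reader might take the 14-day row (50.7%, or 54.0% with ties) as the expected frequency, but the protocol schedules no 14-day response assessments. A reader might also infer a material bias in the PFS or duration-of-response estimates. That needs the number of partial dates, which is not given and is probably small.

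**What to change.** Replace the comparison clause in the on-study progression rule with three ordered steps:

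1. Take the later of the 1st of the month and the day after the latest of: randomization (first dose in the cohorts whose PFS starts there); the last adequate non-progression assessment preceding the progression record; and, for responders, the first documented response.
2. Cap the result at the last day of the recorded month.
3. Take the minimum of that and the death date.

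Restricting step 1 to assessments before the progression record, together with the cap, stops a later clean laboratory visit after clinical or imaging progression from pushing the date beyond the recorded month. The SAP already defines an adequate assessment for myeloma subjects, and its death rule already uses a floor.

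The floor removes impossible dates, but not all of the early shift. It also leaves the Table 1 reclassification possible when no anchor falls in the progression month, so the imputed cases should be listed. The cost is one clause of SAP text and a small programming change; no new data are needed.

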**Table 1: Censoring Scheme for Primary and Sensitivity Analysis PFS**

Situation	Primary	Sensitivity
No progression per response criteria, no death and no subsequent anticancer therapy	Censored on the date of last tumor assessment	Censored on the date of last visit date
No progression per response criteria, no death and with subsequent anticancer therapy	Censored on the date of last tumor assessment prior or on the date of initiation of the subsequent anticancer therapy	Censored on the date of last visit prior or on the date of initiation of the subsequent anticancer therapy
Progression per response criteria without a subsequent anticancer therapy started	Event on the date of the first documented tumor progression per response criteria	Event on the date of the first documented tumor progression per response criteria
Progression or death after a subsequent anticancer therapy started	Censored on the date of last tumor assessment prior or on the date of initiation of the subsequent anticancer therapy	Censored on the date of last visit prior or on the date of initiation of the subsequent anticancer therapy
Death without progression per response criteria and without subsequent anticancer therapy started	Event on the date of death	Event on the date of death

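### SAP Section 8 lets an imputed start of subsequent therapy fall before documented progression, and Table 1 then censors a true primary-PFS event

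*SAP*

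**What the plan says.** SAP Section 8 opens with a general reference: "In general, EmBARC standard time windowing, imputation rules, and counting rules will be applied". It then sets out rules by type of date.

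- Death, day missing: the 1st of the month, with a floor. "The imputed date will be compared to the last known alive date and the maximum will be considered as the death date".
- On-study progression, day missing: the 1st of the month, with a ceiling. "The minimum of the imputed progression date and date of death will be considered as the date of progression".
- Progression on prior therapies: its own rule.
- Everything else: "For other partial/missing dates, the following conventions were used". With the day missing, "the 15 th of the month will be used to replace the missing day". For a year-only date: "If both the day and the month are missing, “July 1” will be used to replace the missing information".

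The start of subsequent therapy is not named, so it belongs to the last group, which has no floor or ceiling.

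SAP Table 1 uses that start date to choose between two opposite outcomes for a subject with documented PD. PD with no subsequent therapy begun is an event at first documented progression. The row "Progression or death after a subsequent anticancer therapy started" is censored at the last tumor assessment (primary column) or last visit (sensitivity column) up to the start of that therapy.

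**The concern.** PFS status in this plan depends on three dates: progression, death and start of subsequent therapy. Section 8 protects the first two against impossible orderings and leaves the third to a mid-month or mid-year default. New therapy commonly follows progression, so a default date can easily land on the wrong side of PD. The subject then moves from the event row of Table 1 to the censoring row because of the imputation alone.

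A subject can lose an event this way only after progressing, so the censoring is informative. Table 1's sensitivity column contains the same row and cannot reveal the problem. The Cohort B arms are planned at about 40 and 20 subjects, so a single reclassified event can visibly move a Kaplan-Meier estimate.

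**Working it through.** The documents give no figure on this point, so there is none to reproduce. The check applies the Section 8 rule to known true dates and then reads off the Table 1 row.

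**Worked cases (illustrative dates)**

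1. PD 10-Sep-2019, therapy 08-Oct-2019, recorded as 2019. Imputed start is 01-Jul-2019, which is 30 + 31 + 10 = 71 days before PD. Table 1 censors on or before 01-Jul and the event is lost.
2. PD 20-Mar-2019, therapy 28-Mar-2019, recorded as Mar-2019. Imputed start is 15-Mar, 5 days before PD. The event is lost.
3. PD 05-Mar, therapy 28-Mar, recorded as March. Imputed start is 15-Mar, after PD. The event is kept.

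**How often, given a partial date**

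Assumptions: PD dates uniform over 2018-2021 (1,461 days, one leap year); true therapy start *g* days after PD.

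*Day and month missing.* The event is lost when PD is on or after July 2 and therapy starts in the same calendar year. That is 183 − g days per year, so the share is 4 × (183 − g) / 1461.

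*Day missing.* The event is lost when PD is on the 16th or later and therapy starts in the same month. In a month of L days that is max(0, L − 15 − g) days, so the gap can be at most 15 days. At g = 7, a 31-day month contributes 9 days, a 30-day month 8, and February 6 (7 in the leap year). A common year gives 7×9 + 4×8 + 6 = 101 and the leap year 102, so 3×101 + 102 = 405 days in total.

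| Gap from PD to therapy | Day missing | Day and month missing |
|---|---|---|
| 1 day | 693/1461 = 47% | 728/1461 = 50% |
| 7 days | 405/1461 = 28% | 704/1461 = 48% |
| 14 days | 72/1461 = 5% | 676/1461 = 46% |
| 21 days | 0% | 648/1461 = 44% |
| 28 days | 0% | 620/1461 = 42% |
| 56 days | 0% | 508/1461 = 35% |
| 84 days | 0% | 396/1461 = 27% |

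**The opposite error**

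Suppose therapy truly began g days before PD, so that Table 1 should censor, but the imputed start falls after PD. A false event results.

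- Day missing: 48 × (14 − g) / 1461 for g up to 14. This is 624/1461 = 43% at 1 day, 336/1461 = 23% at 7 days and 0% at 14 days or more.
- Day and month missing: 181 − g days in a common year and 182 − g in the leap year. At 28 days, (3×153 + 154)/1461 = 613/1461 = 42%.

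**With a bound at documented PD**

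If therapy truly followed PD, the imputed start is not allowed to precede PD, and same-day PD counts as an event, the share of events lost is 0% at every gap.

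**The case against.** Several stronger readings are tempting, and the documents do not carry them.

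*That a missing day alone is a common cause of lost events.* Protocol Sections 3.1 and 5.4.1.2 require two consecutive assessments to confirm progression before new therapy, with laboratory assessments every 4 weeks. Table 1 dates PD at first documentation. If confirmation waits for the next scheduled assessment, the gap is about 28 days and the day-missing route yields 0%. No minimum confirmation interval is visible, so early repeats remain possible, but this route should be uncommon.

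*That partial dates are frequent here.* Nothing in the documents says so. Protocol Section 5.4.1.2 follows subjects for subsequent therapy at least every 12 weeks after progression, which should keep year-only dates rare.

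*That PFS is biased upward.* Lost events push that way, but false events push the other. The protocol foresees therapy before PD: Section 3.5.1 keeps such subjects on 4-weekly assessments. The net direction depends on an unknown case mix.

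*That primary DOR loses events in the same way.* The SAP's DOR paragraph applies the subsequent-therapy cut-off to subjects alive without progression and borrows the PFS scheme only for its sensitivity analysis. The PFS prose is similar, but Table 1 settles the matter for PFS. No table does so for primary DOR, so the effect there is unclear.

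Two further points are fair. The EmBARC standards might contain a bound, but their content is not given, and the explicit catch-all is what the SAP states. PFS is also a secondary endpoint in a cohort not powered for hypothesis testing, where safety is primary.

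These points limit size and scope. They do not alter the result of following Section 8 and Table 1 as written.

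**Conclusion.** The defect stands, with limited scope. Applied as stated, the catch-all can place the start of subsequent therapy before a documented PD, and Table 1 then records a true primary-PFS event as censored in both columns.

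The main exposure is the July 1 rule: about 42% of year-only dates at a 28-day gap, or roughly one lost event for every 2.4 such dates (1461/620). The day-missing route exists only for gaps up to 15 days. Both figures assume uniform PD dates and a fixed gap, and both are conditional on a partial date. The overall effect on PFS therefore cannot be sized, and no net direction of bias can be claimed.

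The secondary (ITT) PFS definition does not censor at subsequent therapy and is unaffected. Comparing it with the primary analysis would help expose reclassified cases, but would not correct them. Sensitivity DOR and duration of MRD negativity also use this date. The correction is worth making, although it does not touch the primary safety endpoint.

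**What to change.** Add a named rule to SAP Section 8 for the start of subsequent therapy:

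- Impute within the recorded month or year. Where the recorded part allows, set the date no earlier than the day after last study dose and no earlier than documented PD, unless the CRF shows that therapy began before PD.
- State that PD on the same day as the imputed start is an event.
- List every subject with an imputed start, and report a sensitivity analysis using the earliest and latest dates compatible with what was recorded.

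The limit to the recorded month or year matters: an unconditional floor of PD plus one day would push a March start into April when PD is on 31 March. If the EmBARC standard already holds such a bound, cite it and state that it overrides the catch-all. The SAP should also say whether primary DOR follows the Table 1 row.

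The cost is a few lines of SAP text and some programming. The downside is that truly ambiguous cases default to events; the earliest/latest analysis shows how much that matters.
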